### **Covariates**

In order to increase the precision of our estimates, we include the following individual level covariates, gathered at the point of referral and local authority covariates (where they are available) from the most recent time point preceding the point of referral.

#### Vector of individual level covariates of the child or young person

- Gender (included as a binary indicators for male, female, or other/undetermined)
- Ethnicity
- Age in months
- Academic year
- Disabled status (included as a binary indicator: 0=No, 1= Yes)
- Eligibility for free school meals (included as a binary indicator: 0=No, 1=Yes, if pupil has ever been recorded as eligible for free school meals on Census day in any Spring Census up to the pupil's current year), Pupil Premium eligibility (for Reception, Year 1 and Year 2)
- Is child an Unaccompanied Asylum Seeker (included as a binary indicators, 0=No, 1= Yes)
- Number of previous child protection plans
- The main need for which child started to receive services for this referral (if applicable), as defined in the [CIN census](#) (included as a categorical variable: 0 = Not stated, 1 = Abuse or neglect, 2 = Child's disability/illness, 3 = Parental Disability/illness, 4 = Family in acute stress, 5 = Family dysfunction, 6 = Socially unacceptable, 7 = Low income, 8 = Absent parenting, 9 = Cases other than Children in Need).

In addition, we would have wanted to take into account families (e.g. through adding family fixed effects), however we are reasonably confident data will not be available, so we have refrained from including them.

---

 In the categories defined in the DfE's CIN census.

 We use Pupil Premium Eligibility for the first three years as every child is eligible for free school meals during this period.

 UN High Commissioner for Refugees (UNHCR). (2013, March). *UNHCR's Engagement with Displaced Youth*. <https://www.refworld.org/docid/5142d52d2.html>, p28.

### Vector of time-varying local authority level covariates

- Number of children in the local authority
- Numbers of assessments by Children's Social Care
- Average number of cases per children and family social worker (based on full-time equivalent (FTE) counts) as defined in the [Local Authority Interactive Tool](#) (LAIT) (integer)
- Proportion of children / young people not seen in accordance with the timescales specified in the plan (continuous variable)
- Proportion of children / young people eligible for Free School Meals (continuous variable)
- Proportion of children / young people white British (continuous variable)
- Turnover rate of staff (percentage rate)
- Presence of other Innovation Programmes - if the authority used programmes additional to Family Safeguarding that had similar aims or that induced whole system change (e.g. Signs of Safety) (coded as binary variables)

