## Participants

The children that we include in our sample are those who meet the following criteria.

- They are referred to the local authorities' children's services. This is a rather broad baseline population which we use because the implementation of Family Safeguarding can potentially lead to changes in assessment thresholds.
- Their original referral date falls within the trial period as defined above.
- Are aged 0-12 at the time of referral. This is the primary age group that the Family Safeguarding teams in the developer local authority Hertfordshire work with. While Safeguarding teams can in theory work with adolescents as well, safeguarding concerns among adolescents are more likely to become contextual which in some local authorities are specifically addressed by adolescent teams. Since the Family Safeguarding model also focuses on work with parents, the implementation is likely to have a larger effect on children up to the age of 12 than on young people.

This will provide our analytical sample, which will then be further restricted or extended for different outcomes, as described in the RCT Design Table above and in the 'Outcome measures' section below.

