## Analysis plan

### Primary Analysis

We will assess the impact of Family Safeguarding Model on the primary outcomes of interest  $Y_{iat}$  in the following GLMM regression framework:

$$\text{logit}(Y_{iat}) = \beta_0 + \alpha_{0a} + \beta_1 FS_{iat} + \sum_{i=1}^5 \beta_{i+1} I(t = i) + \gamma X_{iat} + \rho Z_{at} + \varepsilon_{iat}$$

Where

- $Y_{iat}$  is a binary indicator that equals 1 if the child entered care within 24 months of their first referral in the trial period, and 0 otherwise.
- $\alpha_{0a}$  is a (normally distributed) random intercept at the level of the cluster. This random effect estimates the stochastic variation of individual clusters around the conditional mean of the clusters.
- $\beta_2 - \beta_6$  are a series of indicator variables adjusting for time trends by introducing dummy variables for each time after the baseline period  $t = 0$ .
- $FS_{iat}$  is a binary indicator that is equal to 1 if the child had its first referral during the trial period after the local authority implemented Family Safeguarding (and 0 if before).
- $X_{iat}$  is a vector of individual and household level characteristics that may also influence the outcome, such as age of the child, gender, and household SES.
- $Z_{at}$  is a vector of time-varying local authority characteristics, such as the number of children per local authority or the turnover rate of staff.
- $\varepsilon_{iat}$  are the errors at time  $t$  for individual  $i$ .

The GLMM is an extension of the GLM for analysing correlated data. The unit of analysis is at the individual level to optimise the power to detect an effect within the constraints of the project. We use a logistic regression within the GLMM framework to account for the binary nature of our outcome variable and because the baseline rate is low.

We will judge the statistical significance of the treatment effects applying a significance level of 5%. Due to the small number of clusters, we cannot cluster or bootstrap standard errors via any conventional method. However, we will consider whether or not applying a wild bootstrap with a correction for the small number of clusters is appropriate in this instance. Our sensitivity analysis will consider different evaluation approaches that are discussed in detail below.

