### **Secondary Analysis**

For all binary secondary outcomes, namely return to statutory services, progression to care proceedings, and repeat referrals for parental substance misuse, domestic violence or parental mental health as defined in the RCT Design Table above, we will use the same regression specification as for the primary outcome.

For the secondary outcomes CP plan duration, days on CPPs, and unauthorised school absence rates, we will use a linear probability model. Due to the small number of clusters, we cannot cluster or bootstrap standard errors via any conventional method. However, as above, we will consider whether or not applying a wild bootstrap with a correction for the small number of clusters is appropriate in this instance. In the case of unauthorised school absence rates where we will measure children repeatedly at the end of three terms, we include individual random effects in the regression specification as well as indicator variables

---

 We will request monthly data on these covariates from the local authorities. In the case that obtaining this more granular data proves impossible, we will use yearly data as a proxy. We will use the most recently available measurement that took place prior to the referral date.

 as defined in the [Local Authority Interactive Tool](#) (LAIT) (integer)

for the school term and a variable controlling for the time since the relevant referral. Other specifications remain as specified in the primary analysis.

Due to the high number of secondary outcomes, we will use Hochberg multiple comparison adjustments to reduce the risk of finding significant results by chance.

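### The primary model adjusts for authority caseload, assessment volume, staff turnover and timeliness measured mostly after go-live, which can remove part of the effect under study and is unlikely to deliver the intended precision

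*Protocol*

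**What the plan says.** The equation under Primary Analysis carries two covariate vectors: X for the child and Z for the authority. Z "is a vector of time-varying local authority characteristics, such as the number of children per local authority or the turnover rate of staff".

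The protocol lists eight authority-level covariates. Four matter most here: "Average number of cases per children and family social worker", "Numbers of assessments by Children's Social Care", the staff turnover rate, and the proportion of children not seen within the timescales of their plan. On timing, footnote 17 states: "We will use the most recently available measurement that took place prior to the referral date". It plans to request monthly values, with yearly values as a fallback. The Data gathering table lists six-month summaries.

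The purpose is given under Covariates: "In order to increase the precision of our estimates, we include the following individual level covariates", and the authority covariates are included for the same reason, where available.

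Elsewhere the protocol treats some of these quantities as open to change by the model. Participants says that "the implementation of Family Safeguarding can potentially lead to changes in assessment thresholds". The IPE Design Table, under Mechanism, lists staff-reported workload among the things the intervention may be perceived to affect.

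The equations under Differential time effects and High and low readiness both keep Z. Secondary Analysis carries the primary specification over to the other outcomes.

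**The concern.** Research question 1 asks for the impact of Family Safeguarding on the likelihood of becoming looked after, which is a total effect. If the model lowers caseloads or changes how many referrals are assessed, and that in turn alters care entry, those changes are part of the effect. A regression that holds them fixed estimates only what is left over. It can also introduce new bias where a covariate and the outcome share unmeasured causes.

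The stake goes beyond the primary test, because the Cost Benefit Analysis takes its looked-after savings from the same coefficient.

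The protocol shows awareness of the problem elsewhere. Footnote 4 starts the clock for secondary outcome 1 at referral, to avoid selection caused by changed risk assessment. The covariate set has no comparable protection.

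The second strand is precision. In a design with five authorities and six periods, authority-by-period covariates compete with the treatment indicator for the same few cells, so adding them can cost precision. The power calculation makes no allowance for this.

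**Working it through.** **1. Are the values post-go-live for treated children?** The staircase has 5+4+3+2+1 = 15 treated authority-periods.
- Monthly values: 15 × 6 = 90 treated authority-months. At most the first month in each of five authorities carries a pre-go-live value, so at least 85 of 90 are post-go-live.
- Six-month summaries of the preceding period: the first treated period in each authority carries a pre-go-live value, leaving 10 of 15 post-go-live.
- Yearly fallback: a pre-go-live value could serve for up to 12 months, that is up to 2+2+2+2+1 = 9 of 15 cells.

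So most treated children carry post-go-live values under the monthly or six-monthly plan. Under the yearly fallback this is less certain.

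**2. Which covariates can the model change, on the protocol's own account?**
- Assessment volume: linked to the threshold statement in Participants.
- Caseload: linked to workload under Mechanism in the IPE Design Table.
- Turnover and timeliness: plausible for a whole-system reform, but not stated.
- Number of children, free school meals share and white British share: not plausibly changed.

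**3. The stated MDES, reproduced.** Inputs (MDES table and Appendix B): p = 0.06, 1,700 per cell, ICC 0.00722, I = 5, T = 6, two-sided 5%, power 80%. No covariates enter.
- Total variance 0.06 × 0.94 = 0.0564; τ² = 0.00722 × 0.0564 = 0.000407; cell variance σ² = (1 − 0.00722) × 0.0564 / 1,700 = 0.00003294.
- Hussey–Hughes: Var = Iσ²(σ² + Tτ²) / [(IU − W)σ² + (U² + ITU − TW − IV)τ²], with U = 15, W = 55, V = 55. The brackets are 75 − 55 = 20 and 225 + 450 − 330 − 275 = 70.
- SE = 0.00374; MDES = (1.960 + 0.842) × 0.00374 = 0.01048; power at 0.0105 = 80.2%. The stated 0.0105 is confirmed.

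**4. Adding eight authority-level terms.** A rough guide: 30 cells − 5 authorities − 5 further periods = 20 dimensions, treatment included. Eight arbitrary terms leave 12, so the SE rises by √(20/12) = 1.29.

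The same generalised least squares model was then run with eight simulated covariates unrelated to outcome and treatment. Their patterns are assumed, because the document gives none. Results are medians, with MDES = ratio × 0.01048 and power = Φ(0.0105 / (ratio × 0.00374) − 1.96).

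| Data | SE ratio | MDES | Power at 0.0105 |
|---|---|---|---|
| Monthly, pure noise | 1.02 | 0.0107 | 78% |
| Monthly, slowly drifting | 1.17 | 0.0123 | 67% |
| Six-monthly, noise or random walk | 1.28–1.29 | 0.0134–0.0135 | 59% |

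Six-monthly values that barely move within an authority (autocorrelation 0.99) gave 1.17, close to the drifting monthly case.

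**5. Could the terms pay for themselves?**
- By explaining between-authority variance, hardly: cutting the ICC from 0.00722 to 0.001 moves the unadjusted MDES only from 0.0105 to 0.0102.
- By explaining authority-by-period variance, possibly. With an assumed cluster autocorrelation of 0.9, the MDES is 0.0156 unadjusted, 0.0169 if the terms explain half of that variance and 0.0152 if they explain three quarters. At 0.8 the figures are 0.0192, 0.0197 and 0.0168.

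**6. Mediation, by assumption only.** If 10%, 25% or 50% of a 1.05-point effect ran through the covariates, the adjusted effect would be 0.945, 0.79 or 0.525 points. Power at the planned SE would be 71%, 56% or 29%. The document gives no basis for choosing among these.

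**The case against.** - **Precision.** A reader might infer that the eight terms must cut precision and that true power is about 59%. The documents do not support this. That figure belongs to six-monthly values, whereas footnote 17 aims for monthly data, where the loss may be as small as 2%. The simulated covariates are unrelated to the outcome by construction, and step 5 shows that a gain is possible. The count of eight is not settled either, since covariates enter where available and are dropped above 30% missing.
- **Mediation.** The IPE Design Table also lists average caseload among assumptions and facilitating factors, measured from before implementation, so there it is treated as context. Intention to remain sits under staff experience, not under Mechanism. No passage says that the model changes turnover or timeliness.
- **Main need.** Its definition refers to the start of services, which might suggest that it is recorded after implementation has had its influence. But Covariates says that child-level covariates are gathered at the point of referral. This is an ambiguity, not an established error.
- **Scope.** Deleting the whole vector would remove the other-programmes indicators on which the Risks section relies against unanticipated changes in authorities. With five authorities that protection matters.

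All four limits stand. They narrow the point, but they do not answer it for caseload and assessment volume, where the protocol itself indicates a pathway and plans no analysis without the adjustment.

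**Conclusion.** The point holds in a limited form. As specified, the primary coefficient is not safely the total effect asked for in research question 1, because the model conditions on caseload, assessment volume, turnover and timeliness at values that are mostly post-go-live for treated children. The evidence is firmest for assessment volume and caseload. For turnover and timeliness it rests on plausibility. The size of the resulting bias cannot be computed from the document.

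The precision rationale is doubtful but not refuted. Under the protocol's variance model (a random authority intercept only) and with unrelated covariates, the MDES moves from 0.0105 to roughly 0.0107–0.0123 with monthly data, or about 0.0134–0.0135 with six-monthly data unless these barely change. A net gain would require the terms to explain most of an authority-by-period variance that the protocol does not model. In either case the stated 80% power makes no allowance for these terms.

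**What to change.** In the primary model, and in the secondary models that share its specification:

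1. Replace caseload, assessment volume, turnover and timeliness by each authority's pre-trial value, or remove them.
2. Keep the other-programmes indicator and, if wanted, the covariates that the model cannot plausibly change: number of children, free school meals share and ethnic mix.
3. Use main need only if it is confirmed as fixed at referral. Otherwise move it to the sensitivity analysis.
4. Report the full time-varying authority set as a labelled sensitivity analysis.
5. Include the retained authority-level terms in the power simulations that the protocol already promises.

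The cost is small: a few terms change in one equation, and no new data are needed beyond pre-trial values if those are used. The downside is less adjustment in the primary model for unrelated shocks to caseload and staffing. The sensitivity analysis would still show how far these matter.

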### **Handling missing data**

In cases of missing data, we will consider the possible reasons for its missingness and undertake statistical analyses to determine whether there are any patterns relating to other recorded covariates or to the intervention variable. We will drop observations with missing outcome variables, and will drop covariates that are missing at a rate greater than 30%. For covariates with lower levels of missingness, we will conduct null imputation, by which we mean, for categorical variables, creating an additional dummy variable for the covariate indicating whether it is missing or not; for numeric variables, we will do the same, but also, in the numeric covariate, code it as another arbitrary number - e.g. 0 (that will be the same for all such missing values).

### **Secondary Analysis**

For all binary secondary outcomes, namely return to statutory services, progression to care proceedings, and repeat referrals for parental substance misuse, domestic violence or parental mental health as defined in the RCT Design Table above, we will use the same regression specification as for the primary outcome.

For the secondary outcomes CP plan duration, days on CPPs, and unauthorised school absence rates, we will use a linear probability model. Due to the small number of clusters, we cannot cluster or bootstrap standard errors via any conventional method. However, as above, we will consider whether or not applying a wild bootstrap with a correction for the small number of clusters is appropriate in this instance. In the case of unauthorised school absence rates where we will measure children repeatedly at the end of three terms, we include individual random effects in the regression specification as well as indicator variables

---

 We will request monthly data on these covariates from the local authorities. In the case that obtaining this more granular data proves impossible, we will use yearly data as a proxy. We will use the most recently available measurement that took place prior to the referral date.

 as defined in the [Local Authority Interactive Tool](#) (LAIT) (integer)

for the school term and a variable controlling for the time since the relevant referral. Other specifications remain as specified in the primary analysis.

Due to the high number of secondary outcomes, we will use Hochberg multiple comparison adjustments to reduce the risk of finding significant results by chance.

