	sample	Children aged 0-12 that have been referred within the trial period and that also started a CPP plan within 12 months of the initial referral start date.
Secondary outcome 3	variable	Days on CPPs
	measure	Discrete variable equal to the number of days that the child has been on CPP plans over a period of 36 months from initial referral.
	sample	Children aged 0-12 that have been referred within the trial period.
Secondary outcome 4	variable	Whether or not the child proceeds to care proceedings
	measure	Coded 1 if the child has started care proceedings following pre-proceedings (under the PLO) within 16 weeks of the first pre-proceedings meeting, and coded 0 if not.
	sample	Children aged 0-12 that have been referred within the trial period and that started pre-proceedings within 18 months of the referral.
Secondary outcome 5	variable	Repeat referrals for parental substance misuse, parental mental health or domestic violence
	measure	Coded 1 if the child has been re-referred within 18 months of an initial referral where the factors identified at the end of assessment included either parental substance misuse, parental mental health, or domestic violence. As measured 18 months after first referral. Coded 0 if not re-referred within 18 months.
	sample	Children aged 0-12 that have been referred within the trial period. The factors identified at assessment must include parental substance misuse, domestic violence, or parental mental health.

Secondary outcome 6	variable	Unauthorised school absence rates
	measure	Continuous variable equal to the percentage of sessions missed due to unauthorised absence out of all the school sessions the child was expected to attend for the three terms that start after the initial referral date.
	sample	Children aged 0-12 that have been referred within the trial period.

We will use administrative, secondary data for the analysis. The administrative data will be provided by each local authority in the evaluation. Local authorities that are participating in the evaluation have committed to providing data. For details please see the Data Gathering section below.

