### **Sample size / MDES calculations**

*NB: These power calculations were conducted with the 'steppedwedge' package in Stata. We will conduct simulations to ensure the accuracy of these and update the trial protocol before any outcome data is collected. This could lead to changes in the minimum detectable effect size (MDES).*

---

 Note that the cases do not need to be open after assessment, i.e. we expand the population of interest beyond our analytical sample for this outcome measure.

	Proportion of children who become CLA within 18 months of referral start date
MDES	0.0105
Baseline measures	0.06
Intraclass correlation (ICC) Local authority	0.00722
Alpha	0.05
Power	0.8
One-sided or two-sided?	Two-sided
Level of intervention clustering	Local authority
Number of clusters	5
Average cluster size (children per local authority across all time periods)	10,200
Average cluster cell size (children per local authority per time period)	1,700
Sample Size (children) Total	51,000

We are powered to detect an effect size of 0.0105, or a 1.05 percentage point decrease or increase in the proportion of children who become looked after within 18 months of referral start date.

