## Appendix B: Power calculations Stata code

```
steppedwedge, binomial detectabledifference complete(1) vartotal(0) p1(0.06) m(1700) k(1)  
rho(0.00722) alpha(0.05) beta(0.8) steps(5)
```

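### The school-absence model (secondary outcome 6) leaves out the child's pre-referral absence, giving up a precision gain of a size the protocol does not fix

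*Protocol*

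**What the plan says.** The RCT Design Table (Protocol, Design) defines secondary outcome 6 as a "Continuous variable equal to the percentage of sessions missed due to unauthorised absence", taken "for the three terms that start after the initial referral date". The Outcome measures section words the start of the first term slightly differently, but it says the table takes precedence, so every absence measurement follows referral.

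Secondary Analysis gives this outcome individual random effects and indicator variables "for the school term and a variable controlling for the time since the relevant referral. Other specifications remain as specified in the primary analysis". That carries over the authority random intercept, the five period dummies and the two named covariate lists.

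The Covariates section gives the purpose of the lists: "In order to increase the precision of our estimates, we include the following individual level covariates, gathered at the point of referral". The individual list has gender, ethnicity, age, academic year, disability, free school meals or Pupil Premium, asylum status, main need, and one item of service history, "Number of previous child protection plans". Neither list contains earlier absence.

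Handling missing data drops covariates missing at a rate above 30% and uses a missing indicator below that. Outcome measures calls the absence outcome exploratory. Secondary Analysis includes it in the Hochberg adjustment.

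**The concern.** A child's own earlier absence is the natural predictor of later absence, and the stated aim of the covariates is precision. The lists carry history relevant to the child protection plan outcomes but nothing equivalent for absence. Because the protocol names the lists and carries them over, this is a choice already made and not a detail left for later.

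The child random effect does not replace a baseline value. All measurements follow referral and treatment is fixed for each child, so the random effect models correlation within a child but explains none of the between-child variance that enters the treatment contrast.

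Two things are at stake for research question 6: precision, and protection against a change in the prior absence of referred children at the time an authority goes live. The Participants section says the intervention may change assessment thresholds, and the Risks table lists threshold changes as a possible source of bias, so such a change is conceivable.

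**Working it through.** **The protocol's own power figure.** The only one is for the primary outcome: "We are powered to detect an effect size of 0.0105". Appendix B gives the inputs as "p1(0.06) m(1700) k(1" and "rho(0.00722) alpha(0.05) beta(0.8) steps(5". With 5 authorities, 6 periods, 1,700 children per cell, total variance 0.06 × 0.94 and ICC 0.00722, the standard stepped-wedge variance gives SE = 0.003739. The detectable difference is (1.960 + 0.842) × 0.003739 = 0.01048, which matches 0.0105. The layout is therefore reproduced and can be reused. Nothing is stated for outcome 6 that could be reproduced.

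**Assumptions for outcome 6** (none is in the protocol):
- 80% power without the baseline term, two-sided 5%.
- Term-to-term correlation r of 0.2 to 0.5, equal between all pairs of terms.
- A baseline value for every child.
- The listed covariates do not already explain prior absence.

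**Step 1: no authority-by-period variation.** The correlation of one baseline term with the mean of three later terms is R = r × √(3/(1 + 2r)). The variance factor is 1 − R². Power is Φ(2.802/√(1 − R²) − 1.960).

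| r | R | Variance factor | Power | Gain (points) |
|---|---|---|---|---|
| 0.2 | 0.29 | 0.91 | 83% | +3 |
| 0.3 | 0.41 | 0.83 | 87% | +7 |
| 0.5 | 0.61 | 0.63 | 94% | +14 |

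**Step 2: stepped-wedge layout with authority-by-period variation.** Generalised least squares on 5 authorities × 6 periods. With total variance 1 and ICC 0.00722, a share d of the authority-level variance is authority-by-period and is not explained by the covariate. The child-level part is (1 − ICC)/m, multiplied by 1 − R² once the baseline is added. Gains in points are shown for m = 1,700 and m = 1,000 per cell, the smaller value allowing for children not in school.

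| d | r = 0.2 | r = 0.3 | r = 0.5 |
|---|---|---|---|
| 0 | 3.4 / 3.3 | 6.7 / 6.6 | 14.3 / 14.2 |
| 5% | 2.1 / 2.4 | 4.1 / 4.8 | 9.1 / 10.7 |
| 10% | 1.5 / 1.9 | 2.9 / 3.8 | 6.5 / 8.4 |
| 20% | 0.9 / 1.3 | 1.9 / 2.6 | 4.1 / 5.9 |

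With an assumed ICC of 0.02 and d = 20%, the gains at r = 0.3 and 0.5 are only 0.8 to 2.8 points. With d = 0 the ICC hardly matters. A higher ICC therefore shrinks the gain only when some of the authority-level variance varies by period.

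**Step 3: how many children lack a baseline.** Assume ages are evenly spread.
- One year out of the nine school ages 4 to 12 gives 1/9 = 11%.
- Under the table's definition a child referred within about a year before starting school can still contribute outcome terms. Adding the unfinished first term gives about 1.33 years out of roughly 9.5, or 14%, taking school entry at about 4.5 years.
- Counted over the whole stated sample aged 0 to 12, ages 0 to 3 alone are 4/13 = 31%, just above the 30% threshold for dropping a covariate.

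**The case against.** The strongest reply is that nothing here is invalid. Leaving out a precision covariate does not bias a correctly specified estimate. The outcome is exploratory, has no direct link in the logic model, and is one of six secondary outcomes. That stands, and it limits the weight of the point.

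A reader might infer a firm loss of 7 to 14 power points. The documents do not support that. It is the result for r of 0.3 to 0.5 from an assumed 80% power with no authority-by-period variation. The protocol states none of these quantities, and the ICC is borrowed from a binary outcome. With five authorities, authority-level variation and small-cluster inference may limit research question 6 more than child-level noise does. Free school meals, age, main need and previous plans may also already carry part of the information.

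A reader might also infer that any difference in prior absence between treated and control children passes straight into the treatment estimate. That is too broad. The authority intercept absorbs most stable differences between authorities at this cell size, the period dummies absorb common trends, and each authority is also its own control. What remains is a within-authority shift that coincides with go-live, beyond what the listed covariates capture. Sampling all referrals guards against threshold changes at later stages, but it does not measure whether the mix of referred children has changed. The protocol raises threshold change as a risk without showing that such a shift will occur.

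The reply is also right that the 30% rule could remove the new covariate if it is assessed over all ages, so the amendment has to settle that.

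**Conclusion.** The point holds as a cheap improvement to an exploratory secondary outcome. The outcome 6 model has no pre-referral absence, which sits poorly with the stated precision aim when the same variable is already requested for three later terms.

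The size is conditional on 80% starting power at two-sided 5% and on the assumed correlations: about +3 to +14 points without authority-by-period variation, and about +1 to +6 points if 20% of the authority-level variance is authority-by-period at ICC 0.00722. It is smaller again if a higher ICC accompanies that variation, or if the existing covariates already explain prior absence.

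On bias, only a within-authority shift in prior absence at go-live stays uncorrected. The documents do not show that the estimate for research question 6 is biased, and the primary conclusion is not affected.

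**What to change.** In Secondary Analysis, for secondary outcome 6 only, add as a covariate the child's unauthorised absence rate in the last completed school term before the referral date. Use the existing missing-indicator rule for children with no prior school term. State that the 30% drop rule for this covariate is assessed among children with an observed absence outcome. Add that one term to the individual-level request under Data gathering, before the data template goes to the authorities.

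The cost is two or three sentences and one more term of a variable already requested. The downsides are a slightly larger data request and no baseline value for roughly 11 to 14% of children with an absence outcome if ages are evenly spread. The protocol does not say whether pre-referral absence can be obtained, so this should be confirmed when the template is discussed with the authorities' data teams.
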